3. DESCRIPTION OF RESEARCH PROTOCOL

A. Study Design – Overview, Methods, Procedures

Overall study design:

Patients diagnosed with chronic migraine (fulfill criteria for CM as defined in the ICHD-3 beta), especially those complaining about chronic muscle tenderness, are routinely considered good candidate to benefit from a surgery in which trapped nerves are decompressed. In routine clinical care, such patients are referred to [name] (plastic surgeon performing these procedures) to determine whether or not they fit to undergo the nerve decompression procedure. Of great importance to the evaluation of the proposed study is the fact that the decision on whether or not to operate is unrelated to and independent of any academic study. Those deemed good candidate for the surgery, which include fulfilling all inclusion/exclusion criteria, would be presented with an option to hear about the study from a research nurse. Those interested in hearing about the study will be presented with all the necessary details required and then given the option to sign (or not to sign). They will be given as much time as needed to sign the consent form and have the option to take the consent form home and call in interested.

Since the surgery itself is unrelated to the proposed study, all patients (those who sign the informed consent and those who chose not take part in the study) are booked for the surgery. Usual waiting time is 3-6 month.

Those who agree to participate in the study, will be asked to fill out a 15min headache questionnaire that contains questions about their headaches. Subjects will also be asked to complete a headache diary 3 months prior to botox injections.

Enrolled subjects will be booked for another visit to [name] clinic 30 days prior to their planned surgery. In this visit, they will be injected with 40 units of Botox in one side of their head/neck as detailed below.

During surgery, calvarial periosteum, pericranial muscles and fascia surrounding nerves that are routinely removed and discarded, will be collected by [name], stored in in RNAlater Solution, Ambion, CA, de-identified, frozen, and shipped overnight to [name] lab at BIDMC, where each sample will be recorded, verified, prepared for processing, and analyzed for targeted transcriptome and epigenome involved in inflammatory and immune responses.

Clinical Site Study Procedures

The following research study activities will take place exclusively at MGH:

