Those who agree to participate in the study, will be asked to fill out a 15min headache questionnaire that contains questions about their headaches. Subjects will also be asked to complete a headache diary 3 months prior to botox injections.

The headache diary will be filled out every day for 3 months prospectively prior to botox injection. Subjects will indicate whether they had migraines that day (check date box), what severity the migraines were (on a scale of 0-10), what the duration was (hours), what the location was, which other symptoms they experienced, which medications they took, how often they went to the ED, saw doctors or missed work and how much the total cost was. The total time spent every day filling out the diary should not exceed 5min.

Enrolled subjects will be injected with Botox on one side of the back of the head. The FDA-approved injection paradigm includes 7 muscles (Frontalis, Corrugator, Procerus, Occipitalis, temporalis, Trapezius, and the Cervical Paraspinal muscle group), 31 sites and 155 units divided as follows: Frontalis – 4 sites, 5 units in each; Corrugator – 2 sites, 5 units in each; Procerus – 1 site, 5 units; Occipitalis – 6 sites, 5 units at each; Temporalis – 8 sites, 5 units in each; Trapezius – 6 sites, 5 units at each; Cervical

Paraspinal – 4 sites, 5 units in each.

Of these muscles, sites and doses, patients will be injected (from a 100 Unit vial of OnabotulinumtoxinA reconstituted per product manufacturer label instructions) as follows:

- (A) 2 sites in the Occipitalis muscle (5 units each)
- (B) 4 sites in the Cervical Paraspinal muscle group (5 units each)
- (C) 2 sites in the Trapezius muscle (5 units each)

These injections will be given into one side only. This deviates from the standard of care, as Botox is usually injected on both sides if pain is experienced on both sides. The selection will be random based on subject number. Odd numbers will be injected on the right and even numbers on the left.

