Statistical power analysis: In doing the power calculation, we control for false discovery rate (FDR), a common method used in genome level analysis to control for multiple testing of a large number of genes. The statistical power is also a function of proportion of non-differentially expressed genes using the method developed by Liu and Hwang in 2007. Based on our feasibility study findings, we used 98% non-differentially genes and effect size of 1.5 for power calculation. With 50 chronic migraine (each serving as his/her own control), we will have 95% statistical power to detect effect size of 1.5, with stringent FDR of 0.001.

Figure 2. Power vs. Sample Size with $fdr=0.001$ and $\Delta/\sigma=1.5038$

Statistical analysis for main outcome measure: (A) Comparisons of targeted transcriptome from periosteal, muscles and fascia surrounding nerves will be performed between corresponding injected and not-injected tissues using Wilcoxon's Matched Pairs Tests.

Quality controls (QC), normalization and preprocessing analysis of genomics profiling data : Tissues genomics profiling data will be analyzed using the following major steps:

- (a) Quality control: We will first assign a quality measure for each sample based on nanostring standard QC criteria such as FOV counted, binding density, array mean signal, average background, and scaling factor using expert bioinformatician supervision. We will also check for reproducibility of the samples using correlation and signal-to-noise ratio (SNR) methods for replicate arrays. Low quality arrays will be excluded from further analysis.
- (b) Normalization: Normalization is the most critical step in the analysis, which is a transformation of signal values so that different chip results become comparable. The normalization will be performed in three steps: (i) Positive Spike in controls based normalization that will take care of signal variation due to different amounts of input RNA, (ii) Negative Spike in controls based background correction, (iii) Normalization based on signal values of house keeping genes from the experiments to bring all

the chips onto a similar expression level. The different normalizations and QC's will be performed using the Bioconductor R packages workflows.

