Those who agree to participate in the study, will be asked to fill out a 15min headache questionnaire that contains questions about their headaches. Subjects will also be asked to complete a headache diary 3 months prior to botox injections.

The headache diary will be filled out every day for 3 months prospectively prior to botox injection. Subjects will indicate whether they had migraines that day (check date box), what severity the migraines were (on a scale of 0-10), what the duration was (hours), what the location was, which other symptoms they experienced, which medications they took, how often they went to the ED, saw doctors or missed work and how much the total cost was. The total time spent every day filling out the diary should not exceed 5min.

Study subjects will be injected with Botox on one side of the back of the head. The FDA-approved injection paradigm includes 7 muscles (Frontalis, Corrugator, Procerus, Occipitalis, temporalis, Trapezius, and the Cervical Paraspinal muscle group), 31 sites and 155 units divided as follows: Frontalis – 4 sites, 5 units in each; Corrugator – 2 sites, 5 units in each; Procerus – 1 site, 5 units; Occipitalis – 6 sites, 5 units at each; Temporalis – 8 sites, 5 units in each; Trapezius – 6 sites, 5 units at each; Cervical Paraspinal – 4 sites, 5 units in each.

Of these muscles, sites and doses, patients will be injected (from a 100 Unit vial of OnabotulinumtoxinA reconstituted per product manufacturer label instructions) as follows:

(A)	2 sites in the Occipitalis muscle (5 units each)
(B)	4 sites in the Cervical Paraspinal muscle group (5 units each)
(C)	2 sites in the Trapezius muscle (5 units each)

These injections will be given into one side only. This deviates from the standard of care, as Botox is usually injected on both sides if pain is experienced on both sides. The selection will be random based on subject number. Odd numbers will be injected on the right and even numbers on the left.

Because the standard surgical procedure involves removal of equal amount of corresponding tissues from both sides of the head, an opportunity is created here to analyze identical Botox-treated and Botox-untreated tissues. Importantly, all analyzed tissues are discarded as a part of the surgery and none is collected for the sake of the study.

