The principal investigator ([name]) will be responsible for monitoring outcomes. No independent monitoring will occur. The principal investigator ([name]) will report adverse events to the IRB in accordance with the IRB adverse event reporting procedures.

The principal investigator is responsible for adherence to all IRB rules and guidelines and for the accuracy and completeness of all forms, entries, and informed consent.

For guidance, refer to the following Partners policies:

Data and Safety Monitoring Plans and Quality Assurance

<http://healthcare.partners.org/phsirb/datasafe.htm>

Adverse Event Reporting Guidelines

PRIVACY AND CONFIDENTIALITY

Describe methods used to protect the privacy of subjects and maintain confidentiality of data collected. This typically includes such practices as substituting codes for names and/or medical record numbers; removing face sheets or other identifiers from completed surveys/questionnaires; proper disposal of printed computer data; limited access to study data; use of password-protected computer databases; training for research staff on the importance of confidentiality of data, and storing research records in a secure location.

NOTE: Additional measures, such as obtaining a Certificate of Confidentiality, should be considered and are strongly encouraged when the research involves the collection of sensitive data, such as sexual, criminal or illegal behaviors.

All participants are given a participation number/ code at the time of enrollment. This code is kept on all data sheets instead of the patient's name. Subject information is only accessible by Partners authorized investigators and will not be shared with outside entities. The final results after statistical analysis will not be shared with any institution.

All clinical study records will be stored in a secure location in the office of [name], as all research activities involving patient data will take place at MGH.

SENDING SPECIMENS/DATA TO RESEARCH COLLABORATORS OUTSIDE PARTNERS

Specimens or data collected by Partners investigators will be sent to research collaborators outside Partners, indicate to whom specimens/data will be sent, what information will be sent, and whether the specimens/data will contain identifiers that could be used by the outside collaborators to link the specimens/data to individual subjects.

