De-identified discarded tissue will be transferred to [name] lab at Beth Israel Deaconess Medical Center for processing and analysis. No personally identifiable data (including name, date of birth, age, and gender) will be shared between the clinical site (MGH) and the processing site (BIDMC).

Specifically address whether specimens/data will be stored at collaborating sites outside Partners for future use not described in the protocol. Include whether subjects can withdraw their specimens/data, and how they would do so. When appropriate, submit documentation of IRB approval from the recipient institution.

Specimens will only be used for this research study. Subjects can withdraw their specimens at any time.

RECEIVING SPECIMENS/DATA FROM RESEARCH COLLABORATORS OUTSIDE PARTNERS

When specimens or data collected by research collaborators outside Partners will be sent to Partners investigators, indicate from where the specimens/data will be obtained and whether the specimens/data will contain identifiers that could be used by Partners investigators to link the specimens/data to individual subjects. When appropriate, submit documentation of IRB approval and a copy of the IRB-approved consent form from the institution where the specimens/data were collected.

Collaborators will not collect specimens or data

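### The injected side is called random but is fixed by odd or even subject number, and no random list or concealment is described

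*Combined protocol and SAP*

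**What the plan says.** Section 3.A of the protocol (Clinical Site Study Procedures) sets the injected side in two sentences: "The selection will be random based on subject number. Odd numbers will be injected on the right and even numbers on the left". The Partners protocol summary (Research Design and Methods) repeats the rule, "Odd numbers will be injected on the right and even numbers on the left", and adds nothing on how it is operated. Section 3.B (Statistical Considerations) does not mention allocation of side.

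On numbering, the summary's Privacy and Confidentiality section says: "All participants are given a participation number/ code at the time of enrollment". Enrolment comes before the three-month diary and the injection visit.

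The main-outcome comparison of the targeted transcriptome "will be performed between corresponding injected and not-injected tissues using" a Wilcoxon matched-pairs test, so each patient is his or her own control. Eligibility (section 3.C) asks for a history of bilateral headache pain and chronic neck-muscle tenderness. It does not ask that the two sides be equally affected.

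**The concern.** A rule that reads the side off the parity of a number is systematic. It would be random only if the numbers were themselves assigned at random, and nothing says so. The texts also name no list, no list-holder and no time at which the side is disclosed.

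The comparison is between two sides of one head. Pairing removes everything the sides share, such as age, medication and disease duration. It does not remove a difference that existed between the sides before treatment. Tissue is collected only at surgery, 30 days after injection, so there is no pre-injection sample to adjust for. The way the side is chosen is therefore the main protection against confusing an existing asymmetry with an effect of Botox.

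The stated hypothesis is that Botox reverses abnormal expression of inflammatory genes. If expression follows the more painful side, injecting the milder side too often would make treated tissue look less inflamed and mimic that reversal. Injecting the worse side too often would hide it.

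**Working it through.** The plan states no figure on this point, so the check is mainly a comparison of texts, with a short calculation for scale.

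**1. Is the rule random?** Both statements of it give the same odd/even mapping. No text on consent, numbering, injection, tissue handling or analysis describes random assignment of numbers, a list or concealment.

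**2. Can the side be foreseen?** Two premises are needed, and neither is stated: that the participation number given at enrolment is the subject number, and that numbers run in sequence. If both hold, the next side is known with probability 1.0, before the next patient consents. Under simple randomisation it could be guessed with probability 0.5.

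**3. Who could know?** Section 3.C and the summary (Research Design and Methods) have the surgeon presenting the study and also handling the discarded tissue. Sections 3.A and 6 give the first approach to a research nurse. On the former reading, one role could foresee the side and later handle the samples.

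**4. Could the sides differ beforehand?** Pain must be bilateral, not equal. The headache questionnaire asks whether two-sided headache usually starts on one side, so some asymmetry is expected.

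**5. What would a given degree of steering do?** Let p be the share of patients injected on the worse side and f the worse-to-milder ratio for a gene that Botox does not change. Then

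mean paired shift (log2) = (2p − 1) × log2 f.

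Both p and f are assumed. A positive shift makes injected tissue look more inflamed.

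| p | f | Shift (log2) | Fold |
|---|---|---|---|
| 0.50 | any | 0 | 1.00 |
| 0.55 | 2 | 0.10 × 1 = 0.10 | 1.07 |
| 0.60 | 1.2 | 0.20 × 0.263 = 0.05 | 1.04 |
| 0.60 | 1.5 | 0.20 × 0.585 = 0.12 | 1.08 |
| 0.60 | 2 | 0.20 × 1 = 0.20 | 1.15 |

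With p = 0.40 (steering to the milder side) the last three shifts keep their size and change sign, which favours the hypothesis.

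**6. How does that compare with the plan's thresholds?** The signature analysis in section 3.B requires at least a 2-fold change, which is 1 on the log2 scale. The largest shift above, 0.20, is one fifth of that, so such a shift alone would not be expected to create a signature gene. The main-outcome Wilcoxon comparison has no fold-change filter, so there a shift enters directly. If paired differences have an SD of 0.8 to 1.2 log2 (assumed), the shifts at p = 0.60 run from 0.05/1.2 = 0.04 SD to 0.20/1.2 = 0.17 SD. The 2-fold case with SD 0.8 is left out because the side difference alone would give an SD of √(1 − 0.2²) = 0.98. If the σ in the plan's power figure is also the SD of paired differences, its design effect is 1.5038 SD.

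**7. What would parity's balance be traded for?** Odd/even gives 25 right and 25 left at N = 50, and 33 and 32 at N = 65. Simple randomisation would give a left-right difference of 10 or more with probability about 0.20 (N = 50) or 0.21 (N = 65). Permuted blocks keep the numbers close.

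**The case against.** The strongest reply is that parity does no harm here. Arrival order has no evident link to which side is worse, so if nobody acts on the number the rule behaves like a random one and balances left and right. Recruitment is by referral, patients may take the consent form home, and all have bilateral pain, so there is little scope to arrange who receives which number. Foreseeability also rests on two unstated premises. All of this stands and keeps the point modest. It does not make the rule random, and it does not supply the concealment that would let a report rule steering out.

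A second reply is that the 2-fold requirement already guards the plan's explicit definition of a differentially expressed gene. That is right for the signature list, but it does not cover the main-outcome Wilcoxon comparison.

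A third is that laterality can partly be checked already. The diary records location and maximum severity daily for three months, and the questionnaire has a pain drawing and the one-sided-onset item. This also stands, although none of these asks which side is usually worse.

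Three stronger readings are tempting, and the documents support none of them:

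- A reader might infer that sides were or will be steered. No text shows this or gives a motive for it.
- A reader might want an inflated false-discovery rate. The plan sets no significance level for the Wilcoxon test, and its Benjamini-Hochberg criterion belongs to the LIMMA analysis with the 2-fold filter, so any such rate would describe a rule the plan does not contain.
- A reader might infer that the laboratory can tell treated from untreated samples by the number. Whether specimens carry the number is not stated, and the Privacy and Confidentiality section says that subject information is not shared outside Partners.

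**Conclusion.** The concern holds in a limited form. The rule is misdescribed: it is systematic allocation by parity, and nothing in the protocol or the summary makes it random or conceals it. This matters because side assignment is the main safeguard against a pre-existing difference between sides, and a steered assignment could not be repaired after surgery.

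The size of any bias cannot be derived from the documents. Under the assumed range it runs from nil to modest, at most about 1.15-fold on average, in either direction. That rests on four assumptions: the two numbering premises, some asymmetry between sides that expression follows, and someone acting on the foreseen side. The change is recommended because it is cheap and specific. The documents do not show that the results would be invalid without it.

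**What to change.** In section 3.A and in the protocol summary, replace the parity sentences with: *The injected side will be assigned by a computer-generated 1:1 list in permuted blocks of varying size, kept by existing staff not involved in enrolment and opened only at the injection visit.*

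Before the side is opened, record which side usually hurts more (left, right or equal). In the report, tabulate it against the injected side, next to the diary location and the questionnaire's laterality items.

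The cost is a list, one baseline item and a little time from someone who does not enrol; the documents do not establish who that would be. Left and right numbers become near-equal rather than exactly equal. N and power do not change. The table is descriptive only: if all 50 patients named a worse side, an exact two-sided binomial test would need a 33:17 split, and a true 60% share would reach p < 0.05 only about 24% of the time. A balanced table would therefore not exclude steering, so the concealed list is the real protection.

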The current standard of care for screening for migraine surgery includes injection of Botox to identify nerve triggers. In the occipital region, botox is either injected unilaterally or bilaterally depending on where pain occurs. When pain occurs bilaterally, Botox is injected on both sides. Subjects included in this study have bilateral occipital pain and would therefore as part of routine standard care be injected on both sides. As per this protocol, subjects will only be injected on one side. The risks of unilateral injection of botox (in addition to the risk of Botox in general outlined by the FDA) include continued pain on the uninjected side and/or injected side and one- sided muscle weakness, one- sided bruising, one sided infection on the injected side. More generally, botox injections may cause the formation of anti-botox antibodies, which may decrease the effectiveness of botox treatment in other areas.

Subjects will be informed that they have the option to be injected with Botox on the uninjected side if any unwanted symptoms are experienced on the uninjected side. The cost of injection on the other side will be covered by the study funds.

Because the standard surgical procedure involves removal of equal amount of corresponding tissues from both sides of the head, an opportunity is created here to analyze identical Botox-treated and Botox-untreated tissues. Importantly, all analyzed tissues are discarded as a part of the surgery and none is collected for the sake of the study.

Note that this injection paradigm does not deviate from the currently approved FDA paradigm and that it is given to chronic migraine patients (i.e., for the indication it was approved by the FDA). Also note that one of the standard clinical criteria that these patients must fulfill in order to qualify for the surgical decompression procedure (which is unrelated to the study) is to demonstrate that they have failed at least 3 attempts to treat their chronic migraine with prophylactics – one of which is Botox. Thus, all those who qualify for the study would have been treated with Botox at least twice before as per the FDA approved protocol.

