Note that one of the standard clinical criteria that these patients must fulfill in order to qualify for the surgical decompression procedure (which is unrelated to the study) is to demonstrate that they have failed at least 3 attempts to treat their chronic migraine with (not necessarily Botox). Thus, all those who qualify for the study would have been treated with Botox at least twice before as per the FDA approved protocol.

Thirty days later, patients will undergo a study-unrelated nerve decompression surgery. This procedure involves the removal of different tissues surrounding trapped branches of the occipital nerve. These tissues include muscles, fascia, and periosteum (discarded tissue). The amount of tissue removed at each area is many folds larger than the amount of tissue needed for sampling (less than the size of 1 grain of rice).

There will be two visits:

Screening visit: Patients will be screened for eligibility. This will be performed during the regular clinical assessment for surgery. The study visit will take 30min. The subject will be asked to complete a 15 min questionnaire and will be asked to fill out a 3m headache diary which may take up to 5min a day.

Preoperative visit: will be injected with Botulinum Toxin. This will take 30 minutes.

There will be further routine clinical visits postoperatively (one week, 3 months and 12 months). However, these visits are not related to the study but are part of regular follow up. No study materials for this study will be collected as part of this visit.

Analysis to be Done at BIDMC

(A) Tissue processing, RNA isolation, genetic processing and mRNA counting will occur in [name] lab at Beth Israel Deaconess Medical Center, Harvard Medical School. Bioinformatics and biostatistics analyses will be conducted at [name] lab at Beth Israel Deaconess Medical Center, Harvard Medical School.

Briefly describe study procedures. Include any local site restrictions, for example, "Subjects enrolled at Partners will not participate in the pharmacokinetic portion of the study." Describe study endpoints.
--

Subjects enrolled at partners will participate in all portions of the study.

For studies involving treatment or diagnosis, provide information about standard of care at Partners (e.g., BWH, MGH) and indicate how the study procedures differ from standard care. Provide information on available alternative treatments, procedures, or methods of diagnosis.

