Describe the plan to be followed by the Principal Investigator/study staff for review of adverse events experienced by subjects under his/her care, and when applicable, for review of sponsor safety reports and DSMB reports. Describe the plan for reporting adverse events to the sponsor and the Partners' IRB and, when applicable, for submitting sponsor safety reports and DSMB reports to the Partners' IRBs. When the investigator is also the sponsor of the IND/IDE, include the plan for reporting of adverse events to the FDA and, when applicable, to investigators at other sites.

NOTE: In addition to the adverse event reporting requirements of the sponsor, the principal investigator must follow the Partners Human Research Committee guidelines for Adverse Event Reporting

The principal investigator ([name]) will be responsible for monitoring outcomes. No independent monitoring will occur. The principal investigator ([name]) will report adverse events to the IRB in accordance with the IRB adverse event reporting procedures.

The information collected during this study will be placed in a research folder, and not added to the patient's medical record unless deliberately requested by the patient. All research folders will be filed in locked cabinets, independent of clinical charts or any other medical record in electronic format. Any magnetic or electronic information will be saved in password-protected computers to which only study staff will have access.

Unanticipated problems involving risks to subjects or others including adverse events will be reported to the PHRC in accordance with PHRC unanticipated problems reporting guidelines.

MONITORING AND QUALITY ASSURANCE

Describe the plan to be followed by the principal investigator/study staff to monitor and assure the validity and integrity of the data and adherence to the IRB-approved protocol. Specify who will be responsible for monitoring, and the planned frequency of monitoring. For example, specify who will review the accuracy and completeness of case report form entries, source documents, and informed consent.

NOTE: Regardless of monitoring plans by the sponsor or others, the principal investigator is ultimately responsible for ensuring that the study is conducted at his/her investigative site in accordance with the IRB-approved protocol, and applicable regulations and requirements of the IRB.

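### Could a control side that is injected before surgery be analysed as untreated because the analysts are never told?

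*Combined protocol and SAP*

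**What the plan says.** Section 3.A (Clinical Site Study Procedures) assigns the side by subject number: "Odd numbers will be injected on the right and even numbers on the left". It lists "continued pain on the uninjected side and/or injected side" among the risks of one-sided injection and tells participants that "they have the option to be injected with Botox on the uninjected side if any unwanted symptoms are experienced on the uninjected side", at the study's expense. The Partners Protocol Summary repeats the offer. Neither place says whether it applies before surgery, after surgery or both. Surgery is 30 days after the study injection.

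Section 3.B compares corresponding tissues that were and were not injected, using Wilcoxon's matched-pairs test. It then fits LIMMA with a Botox/no-Botox indicator and declares a gene at adjusted P < 0.01 with at least a 2-fold change.

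On data flow, the Protocol Summary says "Bioinformatics and biostatistics analyses will be conducted at" a BIDMC laboratory. Its safety-monitoring section says "The information collected during this study will be placed in a research folder". Its privacy section says "Subject information is only accessible by Partners authorized investigators and will not be shared with outside entities". Its section on outside collaborators has a form prompt asking "what information will be sent". The answer begins "De-identified discarded tissue will be transferred to" the BIDMC laboratory, and goes on to bar personally identifiable data.

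**The concern.** All participants have bilateral occipital pain, and section 3.A says routine care would inject both sides, so some will plausibly take up the offer. If that happens before surgery, the control tissue has been exposed. The only written link from participant to treated side is odd or even subject number, which gives the assigned side and not the actual exposure. The privacy wording, taken at face value, suggests that the analysts would not hear of a second injection.

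A pair labelled by assignment would then contribute a treated-minus-untreated difference pulled toward zero. Because section 3.B needs an observed change of at least 2-fold, a gene somewhat above 2-fold could slip below the cut. Without a record of exposure, nobody could count such pairs or test how much they matter.

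**Working it through.** **The plan's own figure.** Section 3.B states 95% power with 50 patients as their own controls, effect size 1.5, 98% null genes and FDR 0.001. By the method it names, the ratio of type I error to power must equal (0.001/0.999) × (0.02/0.98) = 2.043 × 10⁻⁵. For 50 pairs the noncentral t has 49 df and noncentrality 1.5 × √50 = 10.6. The critical value is 4.715 and power exceeds 99.9%. Power of 95% is reached at about 24 to 25 pairs (94.5% and 96.3%). If 1.5 is per-sample SD and the two sides are uncorrelated, the paired effect is 1.5/√2 = 1.06 and power is 99.4%. The 95% is not reproduced for 50 pairs, but that is a separate matter, and it leaves more margin here, not less.

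**What the documents establish about labelling.**

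- *Who labels.* No passage says. Sections 3.A and 7 have the clinical site both inject and collect, so the people who fill the tubes are placed to know the exposure.
- *What travels.* A paired test needs at least a pair code and a side or group label. Section 3.A says each sample is recorded and verified on arrival at BIDMC. Something beyond bare tissue must go with it.
- *What is barred.* Section 8 and the outside-collaborator section bar personally identifiable data. Coded injection status is not on that list.
- *The privacy sentence.* The sentence after it says final results go to no institution. Yet BIDMC runs the statistics and section 9 foresees a published paper, so this paragraph cannot be a literal data-flow rule. The Protocol Summary also calls the study a joint project with a principal investigator at BIDMC, so outside entities need not include BIDMC.
- *How groups are defined.* Both analyses in section 3.B are worded by exposure. An injected side does not meet the definition of untreated tissue.

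**Size if mislabelling did happen.** The documents give neither the rate of second-side injection nor the share of the difference lost. Assume k = 0, 5, 10 or 15 of 50 pairs and a loss L of one half or all. The expected log2 difference becomes (1 − kL/50) × log2(fold). At half loss a true 2.3-fold change has expected value 2.3^0.95 = 2.21 at k = 5, 2.3^0.90 = 2.12 at k = 10 and 2.3^0.85 = 2.03 at k = 15.

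Per-gene thresholds are 0.001 × 0.02 × 0.95/(0.999 × 0.98) = 1.94 × 10⁻⁵ and, at FDR 0.01, 0.01 × 0.02 × 0.95/(0.99 × 0.98) = 1.96 × 10⁻⁴.

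*Wilcoxon test alone, FDR 0.001, power in % (20,000 simulated trials):*

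| Reading of 1.5 | Handling | k=0 | 5 | 10 | 15 |
|---|---|---|---|---|---|
| Paired SD | kept, half loss | 100 | 100 | 100 | 100 |
| Paired SD | kept, full loss | 100 | 100 | 98 | 83 |
| Per-sample SD, zero correlation | kept, half loss | 98 | 95 | 91 | 83 |
| Per-sample SD, zero correlation | kept, full loss | 98 | 88 | 64 | 34 |
| Per-sample SD, zero correlation | pairs removed | 98 | 95 | 86 | 69 |

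*Adjusted P < 0.01 plus 2-fold cut, paired-SD reading, chance of declaring the gene in % (40,000 trials; paired t-test at 1.96 × 10⁻⁴ in place of the moderated t; SD set to log2(fold)/1.5):*

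| True fold | Handling | k=0 | 5 | 10 | 15 |
|---|---|---|---|---|---|
| 2.2 | kept, half loss | 90 | 77 | 59 | 38 |
| 2.3 | kept, half loss | 96 | 90 | 76 | 57 |
| 2.3 | kept, full loss | 96 | 76 | 37 | 8 |
| 2.3 | pairs removed | 96 | 95 | 95 | 93 |
| 2.5 | kept, half loss | 100 | 98 | 94 | 84 |

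At 3-fold, half loss leaves at least 99% on this reading. With one or two affected pairs at half loss, a 2.3-fold gene is declared 94 to 95% of the time. If only a quarter of the difference is lost, the figures are 94% at 5 pairs and 90% at 10. A check simulation agreed with the tabulated figures to within about one percentage point.

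**The case for a change.** The best case for a change is that no passage requires a pre-surgery injection of the control side to be recorded by side and date, carried on the sample label, or handled in the analysis. The offer is open to anyone with unwanted symptoms, is funded by the study, and is foreseeable in people with bilateral pain. Follow-up every four weeks puts a contact at about day 28, before surgery. The nearest safeguard is the investigator's judgement on whether a participant with discomfort continues, and it has no criteria. The resulting bias runs toward no difference, and a flag would cost little.

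The silence is real, and so is the direction of the bias. What does not stand is that the analysts do the labelling, that they receive tissue and nothing else, or that they would be unable to correct the problem. Each depends on an undescribed sample label. The site is also likely to know: adverse events are reviewed at each contact, discomfort is evaluated, and the study pays for the second injection.

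Nor is there one clearly better handling rule. Removing affected pairs selects on control-side symptoms, and it can cost more test power than keeping them (69% against 83% at 15 pairs, half loss, zero correlation, FDR 0.001). Keeping them shrinks the fold change. Section 3.C allows up to 65 patients, so if that ceiling were reached, 65 − 15 = 50 pairs would remain even after removing 15.

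**Conclusion.** No change to the plan is called for. This is missing operational detail that the people running the study can fill sensibly. The analysis is already defined by exposure, the site that injects also collects the tissue, and a coded exposure label is compatible with the bar on identifiable data. Followed as written, section 3.B does not count an injected side as untreated.

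The harm needs three things together: second-side injections before surgery in appreciable number, a material effect on the control tissue by the time of surgery, and labelling by assigned side despite the site's knowledge. The documents establish none of these. If all three held, the Wilcoxon comparison would be little changed in most scenarios; the exceptions combine full loss with 10 or 15 affected pairs, or zero correlation with many affected pairs. The loss would fall mainly on genes moderately above 2-fold: for a 2.3-fold gene at half loss on the paired-SD reading, from 96% to 90%, 76% or 57% with 5, 10 or 15 of 50 pairs affected. These figures rest on assumed rates and losses, normal paired differences and a standardized effect of exactly 1.5 for every gene. Whether and when the second side is injected is a clinical matter and is not judged here.
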